## Liver function parameters

Liver function parameters of interest are total bilirubin (TBL), ALT, AST and alkaline phosphatase (ALP).

The number (%) of subjects with newly occurring or worsening values will be summarized:

- ALT or AST > 3xULN
- ALT or AST > 5xULN
- ALT or AST > 8xULN
- ALT or AST > 10xULN
- ALT or AST > 20xULN
- TBL > 2xULN
- TBL > 3xULN
- For subjects with AST and ALT  $\leq$  ULN at baseline
  - ALT or AST > 3x ULN & TBL > 2x ULN
  - ALT or AST > 3x ULN & TBL > 2x ULN & ALP  $\geq$  2x ULN
  - ALT or AST > 3x ULN & BILI > 2x ULN & ALP < 2x ULN
- For subjects with AST and ALT > ULN at baseline (Bsl)
  - Elevated ALT or AST (\*) & BILI ( $>2x$  Bsl and 2x ULN)
  - Elevated ALT or AST (\*) & BILI ( $>2x$  Bsl and 2x ULN) & ALP  $\geq$  2x ULN
  - Elevated ALT or AST (\*) & BILI ( $>2x$  Bsl and 2x ULN) & ALP < 2x ULN

\* Elevated AST or ALT defined as:  $>3x$  ULN if  $\leq$  ULN at baseline, or ( $>3x$  Bsl or 8x ULN) if > ULN at baseline

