Grade 3	
Hold study treatment.
 
Upon resolution to <math>\leq</math> Grade 1 or baseline, reduce capmatinib <math>\downarrow</math> 1 dose level and resume spartalizumab/placebo at same dose level.
 
If resolved in <math>></math> 7 days, discontinue study treatment.
	
Frequent monitoring of LFTs, (every 2-3 days), until resolved to <math>\leq</math> grade 1. If resolved in <math>></math> 7 days, after discontinuing the subject from capmatinib permanently, the subject should be monitored weekly (including LFTs), or more frequently if clinically indicated, until total bilirubin have resolved to baseline or stabilization over 4 weeks

Grade 4	Mandatory: Discontinue study treatment.	
After permanently discontinuing the subject from study treatment, the subject should be monitored weekly (including LFTs), or more frequently if clinically indicated, until total bilirubin have resolved to <math>\leq</math> grade 1 or stabilization over 4 weeks.

Combined elevations of AST or ALT and Total Bilirubin		
Grade 2 AST and/or ALT with bilirubin $\geq$ Grade 2 (unless Gilbert's syndrome)	Mandatory: discontinue study treatment.	After permanently discontinuing the subject from study treatment, repeat LFTs as soon as possible, preferably within 48 hours from awareness of the abnormal results, then with weekly monitoring of LFTs, or more frequently if clinically indicated, until AST, ALT, or bilirubin have resolved to grade 1 or stabilization over 4 weeks
OR		
For participants with elevated baseline AST or ALT or total bilirubin value:		
[AST or ALT $>$ 3 x baseline]		
OR [AST or ALT $>$ 8.0 x ULN], whichever is lower, combined with [total bilirubin $>$ 2 x baseline AND $>$ 2.0 x ULN] without evidence of cholestasis or hemolysis		

Worst toxicity CTCAE grade	Dose Modification	Recommended Clinical Management
Amylase and/or lipase increased		
Grade 3	
Hold study treatment.
 
Upon resolution to <math>\leq</math> Grade 2 or baseline within <math>\leq</math> 14 days, resume study treatment without dose modification,
 
If resolved in <math>></math> 14 days, reduce capmatinib <math>\downarrow</math> 1 dose level and resume spartalizumab/placebo at same dose level.
	Perform CT scan or other imaging study to assess the pancreas, liver, and gallbladder must be performed within one week of the first occurrence of any $\geq$ Grade 3 of amylase and/or lipase elevation

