### 6.5.2.1 Follow up on potential drug-induced liver injury (DILI) cases

Subjects with transaminase increase combined with total bilirubin (TBIL) increase may be indicative of potential DILI and should be considered as clinically important events.

The threshold for potential DILI may depend on the subject's baseline AST/ALT and TBIL value; subjects meeting any of the following criteria will require further follow-up as outlined below:

- For subjects with normal ALT and AST and TBIL value at baseline: AST or ALT  $> 3.0 \times$  ULN combined with TBIL  $> 2.0 \times$  ULN

- For subjects with elevated AST or ALT or TBIL value at baseline: [AST or ALT > 2 x baseline AND > 3.0 x ULN] OR [AST or ALT > 8.0 x ULN], combined with [TBIL > 2 x baseline AND > 2.0 x ULN]

As DILI is essentially a diagnosis of exclusion, other causes of abnormal liver tests should be considered and their role clarified before DILI is assumed as the cause of liver injury.

A detailed history, including relevant information such as review of ethanol consumption, concomitant medications, herbal remedies, supplement consumption, history of any pre-existing liver conditions or risk factors, should be collected.

Laboratory tests should include ALT, AST, total bilirubin, direct and indirect bilirubin, GGT, GLDH, prothrombin time (PT)/INR, alkaline phosphatase, albumin, and creatine kinase.

Evaluate status of liver metastasis (new or exacerbation) or vascular occlusion – e.g. using CT, MRI, or duplex sonography.

Perform relevant examinations (Ultrasound or MRI, ERCP) as appropriate, to rule out an extrahepatic cause of cholestasis (cholestasis is defined as ALP elevation > 2.0 x ULN with R value < 2 in subjects without bone metastasis, or elevation of ALP liver fraction in subjects with bone metastasis).

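### SAP 2.8.3 picks the combined transaminase-bilirubin rows by baseline AST and ALT only, so a subject with isolated raised baseline bilirubin can be counted without meeting protocol 6.5.2.1

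*SAP*

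**What the plan says.** SAP 2.8.3, Liver function parameters, splits the combined rows into two blocks by baseline transaminases.

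- The first is "For subjects with AST and ALT $\leq$ ULN at baseline". Its leading row is "ALT or AST > 3x ULN & TBL > 2x ULN", and two further rows add ALP at or above, or below, 2x ULN. Baseline bilirubin plays no part.
- The second is "For subjects with AST and ALT > ULN at baseline (Bsl". Here bilirubin is judged against baseline as well: "BILI ( $>2x$ Bsl and 2x ULN". A footnote sets the transaminase limit, including a clause for a value that was at or below ULN at baseline.

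Protocol 6.5.2.1 also has two groups, but bilirubin helps to decide which one applies.

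- "For subjects with normal ALT and AST and TBIL value at baseline": AST or ALT above 3x ULN with bilirubin above 2x ULN.
- "For subjects with elevated AST or ALT or TBIL value at baseline": the transaminase condition is "combined with [TBIL > 2 x baseline AND > 2.0 x ULN", so both bilirubin limits must be exceeded.

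The combined-elevation row of protocol Table 6-3 has a branch with the same three-way trigger, "For participants with elevated baseline AST or ALT or total bilirubin value", and the same two bilirubin limits. That branch is an alternative to another one, Grade 2 AST or ALT with bilirubin of at least Grade 2 (Gilbert's syndrome excepted).

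Inclusion criterion 8 allows total bilirubin below 1.5x ULN. SAP section 4 records no change to protocol-specified analyses.

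**The concern.** The leading row of the SAP's first block has the same limits as the protocol's rule for normal baselines, but applies them to a wider group. A subject with normal AST and ALT and bilirubin somewhat above ULN falls in the SAP's first block and in the protocol's elevated-baseline group. The SAP then asks only for bilirubin above 2x ULN, which such a subject reaches with less than a doubling.

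Enrollment was halted for lack of tolerability. Hepatotoxicity is an adverse event of special interest for capmatinib, and hepatitis for spartalizumab. Under 6.5.2.1, confirmed cases that meet its laboratory criteria and have no alternative cause are reported as SAEs. A reader of the study report is likely to set the combined rows beside those cases, and the two would rest on different baseline rules without the report saying so.

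**Working it through.** Neither document gives a figure to reproduce here. The check sets the rules side by side, with every value in multiples of ULN.

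**Inputs.** Let b be baseline bilirubin, with 1 < b < 1.5: above ULN, and eligible under inclusion criterion 8. Baseline AST and ALT are at or below 1.

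**Transaminase part.** The SAP first block requires AST or ALT above 3. Protocol 6.5.2.1 (elevated group) requires it above 2x baseline and above 3, or above 8. Twice a baseline of at most 1 is at most 2, so the protocol condition also reduces to above 3. The two agree.

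**Bilirubin part.** The SAP limit is 2. The protocol limit is max(2, 2b) = 2b. The SAP therefore counts a subject whom 6.5.2.1 does not when on-treatment bilirubin lies in (2, 2b]. The fold rise needed to pass the SAP limit is 2/b.

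| Baseline b | Protocol limit 2b | SAP limit | Fold rise to pass SAP limit |
|---|---|---|---|
| 1.1 | 2.20 | 2.0 | 1.82 |
| 1.2 | 2.40 | 2.0 | 1.67 |
| 1.3 | 2.60 | 2.0 | 1.54 |
| 1.4 | 2.80 | 2.0 | 1.43 |
| 1.49 | 2.98 | 2.0 | 1.34 |

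**Example.** Baseline AST and ALT 0.8, bilirubin 1.4; on treatment ALT 3.5, bilirubin 2.3.

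- SAP first block: 3.5 > 3 and 2.3 > 2, so counted. The SAP's restriction to newly occurring or worsening values does not remove the subject, because 2.3 is newly above 2.
- Protocol 6.5.2.1: bilirubin must exceed 2 x 1.4 = 2.8, so not met.
- Table 6-3, elevated-baseline branch: the same bilirubin limit of 2.8, so not met.
- Table 6-3, first branch: by the grades in SAP Table 5-3, ALT 3.5 is Grade 2 (above 3 to 5) and bilirubin 2.3 is Grade 2 (above 1.5 to 3). Read literally, it is met.

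**Direction.** Both rules were evaluated on a grid of 3 baseline transaminase values x 6 baseline bilirubin values x 23 on-treatment transaminase values x 70 on-treatment bilirubin values = 28,980 combinations. The SAP alone was met at 3,111, and 6.5.2.1 alone at 0. These counts show direction only; they are not expected numbers of subjects.

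**Where the rules agree.** With AST, ALT and bilirubin all normal at baseline, the SAP row and 6.5.2.1 gave the same answer at every grid point. With both transaminases and bilirubin raised, the SAP never counted a subject whom 6.5.2.1 did not, because its second block already uses baseline bilirubin. The over-count is therefore confined to the first block.

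**The case against.** Four objections have weight.

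- **Table 6-3.** A reader might infer that the SAP conflicts with both protocol definitions. The documents do not support that. The first branch of Table 6-3 is not limited to normal baselines, and its bilirubin grade starts above 1.5x ULN, below the SAP limit of 2. The example meets that branch. Only 6.5.2.1 is a clean comparator.
- **Purpose of the rows.** Section 6.5.2.1 triggers patient follow-up, and protocol 12.5.2.2 specifies no combined transaminase-bilirubin table. The SAP does not label its rows as potential liver injury. Reporting a case as such also needs repeat testing and exclusion of other causes, so the table would not equal the case list even with identical groups. This stands. It limits the consequence, but leaves the leading row using the 6.5.2.1 limits on a different baseline group without explanation.
- **Size.** A reader might take one wrong count as 1/31 = 3.2 percentage points, or assume that several subjects are affected. SAP 2.1 takes percentages over the relevant population or subgroup, and the size of this baseline subgroup is not given. Neither is the frequency of raised baseline bilirubin. Being placed in the wrong block is also not the same as being miscounted: that needs a transaminase above 3x ULN together with bilirubin inside a narrow window.
- **Overall direction.** A reader might infer that the liver summary overstates risk as a whole. That is not shown. A subject with only one of AST and ALT above ULN fits neither block, which is an omission.

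Any error here flags an extra subject rather than hiding one. The baseline-to-worst shift tables will show raised baselines at group level, although they do not correct these rows.

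**Conclusion.** The point holds against protocol 6.5.2.1. For subjects with normal AST and ALT and bilirubin above 1 and below 1.5x ULN at baseline, the SAP's first block uses a bilirubin limit of 2x ULN where 6.5.2.1 uses 2b x ULN. Within this group the discrepancy runs one way, towards over-counting. It touches the leading row and its two ALP sub-rows.

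The size in subjects cannot be derived from the documents and may be zero. An over-count needs at least one treated subject with isolated raised baseline bilirubin whose on-treatment values fall in the window. The rows are descriptive and bear on no efficacy endpoint. This is a wrong grouping rule in a safety table, worth correcting because the correction is nearly free. No view is taken on which clinical threshold is right, in 6.5.2.1 or in Table 6-3.

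**What to change.** In SAP 2.8.3, define the first block as AST, ALT and TBL all at or below ULN at baseline, and the second as AST or ALT or TBL above ULN at baseline. Keep the second block's bilirubin criterion, written out as above 2x baseline and above 2x ULN. The alternative is to keep the present blocks and state and justify the difference from protocol 6.5.2.1 in SAP section 4.

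The redefinition also brings into use the footnote clause for a transaminase at or below ULN at baseline, which cannot apply while the block is restricted to subjects with both values raised. The example would then be judged on ALT above 3x ULN (met) and bilirubin above 2.8x ULN (not met), and would not be counted, in agreement with 6.5.2.1. Subjects with only one raised transaminase would also gain a block.

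The change does not settle the transaminase multiple for raised baselines, on which the SAP footnote and Table 6-3 differ from 6.5.2.1. Those passages need to be reconciled separately.

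Cost: a short wording change and a revised baseline flag in the programming. No new data are needed.

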#### 8.4.5 Laboratory evaluations

The laboratory tests that will be assessed as part of the safety monitoring are listed in [Table 8-5](#). For subjects enrolled in Part 1, all parameters will be analyzed locally. For subjects enrolled in Part 2, hematology, clinical chemistry, coagulation and thyroid parameters will be assessed at a Novartis-designated central laboratory and all other tests will be performed locally.

The frequency of these assessments is indicated in [Table 8-1b](#) or [Table 8-2](#), as applicable. Additional time points should be added as deemed necessary per the investigator's best judgment to make sure the toxicity profile is sufficiently characterized and dose adjustments are performed to safeguard the safety of the subject.

The site does not need to wait for the results of centrally-analyzed laboratory assessments when an immediate clinical decision needs to be made (e.g. confirmation of eligibility, study drug interruption, re-initiation, and/or termination) and in those cases locally unscheduled testing may be performed and used for eligibility assessments. Details on the collection, shipment of samples and reporting of results by the central laboratory are provided to investigators separately in the central laboratory manual.

The results of the laboratory tests performed locally will be recorded in the eCRF, unless differently specified in [Table 8-1b](#) or [Table 8-2](#). Novartis must be provided with a copy of the normal ranges and certification of the all laboratories used to assess subjects' safety during study conduct, when possible. The investigator is responsible for reviewing all laboratory reports for subjects in the study and evaluating any abnormalities for clinical significance.

At any time during the study up to safety follow-up, abnormal laboratory parameters which are clinically relevant and require an action to be taken with study treatment (e.g., require dose modification and/or interruption of study treatment, lead to clinical symptoms or signs, or require therapeutic intervention), whether specifically requested in the protocol or not, will be recorded on the adverse event eCRF page. The severity of laboratory data will be graded using the Common Terminology Criteria for Adverse events (CTCAE) v5.0. (See [Section 10.1](#) for additional information). Additional analyses are left to the discretion of the investigator.

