## **Clinical laboratory evaluations**

All laboratory data will be summarized by subject and visit/time.

Grading of laboratory values will be assigned programmatically as per NCI Common Terminology Criteria for Adverse Events (CTCAE) version 5.0. The calculation of CTCAE grades will be based on the observed laboratory values only, clinical assessments will not be taken into account.

CTCAE Grade 0 will be assigned for all non-missing values not graded as 1 or higher. Grade 5 will not be used.

For laboratory tests where grades are not defined by CTCAE v5.0,

- Shift tables using low/normal/high (low and high) classification to compare baseline to the worst on-treatment value.

The following summaries will be generated separately for hematology and biochemistry tests:

- Listing of all laboratory data with values flagged to show the corresponding CTCAE v5.0 grades if applicable and the classifications relative to the laboratory normal ranges.

For laboratory tests where grades are defined by CTCAE v5.0

- Worst post-baseline CTCAE grade (regardless of the baseline status). Each subject will be counted only once for the worst grade observed post-baseline.
- Shift tables using CTCAE v5.0 grades to compare baseline to the worst on-treatment post-baseline value.

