## 2 Statistical methods

### 2.1 Data analysis general information

Study data will be analyzed by Novartis personnel using the most updated SAS® version in the GPS environment. For analyses using R and/or JAGS (e.g., Bayesian analysis) in the DaVinci environment will be used. PK parameters will be calculated using non-compartmental methods available in the most updated version of Phoenix WinNonlin.

Data from all participating centers in this protocol will be combined by part, so that an adequate number of subjects will be available for analysis. Data will be summarized using descriptive statistics (continuous data) and/or contingency tables (categorical data) for demographic and baseline characteristics, efficacy, safety, pharmacokinetic and pharmacodynamics measurements.

Study data in Part 1 will be reported in the final clinical study report (CSR) based on all subjects' data up to the time of completion of the study. There will be no additional CSR. The final CSR will include all outputs planned within the TFL shells document.

The part 1 of this study has one treatment arm: capmatinib + spartalizumab

**Qualitative data** (e.g., gender, race, etc.) will be summarized by means of contingency tables; a missing category will be included as applicable. Percentages will be calculated using the number of patients in the relevant population or subgroup as the denominator.

**Quantitative data** (e.g., age, body weight, etc.) will be summarized by appropriate descriptive statistics (i.e., mean, standard deviation, median, minimum, and maximum).

Screen failure patients are those who signed the informed consent, but never started the study treatment for any reason. For these patients, the eCRF data collected will not be included in analyses but will be reported in the CSR as separate listings.

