### 2.8.1 Adverse events (AEs)

Adverse event (AE) summaries will include all AEs occurring during on-treatment period. All AEs collected in the AE eCRF page will be listed along with the information collected on those AEs e.g., AE relationship to study drug, AE outcome etc. AEs starting during the post-treatment period will be flagged in the listings.

Adverse events (AEs) will be summarized by number and percentage of subjects having at least one AE, having at least one AE in each primary system organ class (SOC) and for each preferred term (PT) using MedDRA coding. A subject with multiple occurrences of an AE will be counted only once in the respective AE category. A subject with multiple CTCAE grades for the same preferred term will be summarized under the maximum CTCAE grade recorded for the event.

AE with missing CTCAE grade will be included in the 'All grades' column of the summary tables.

In AE summaries by primary SOC and PT, the primary SOC will be presented alphabetically and the PT will be sorted within primary SOC in descending frequency. Table by either primary SOC or PT will be sorted in descending frequency.

The following adverse event summaries will be produced for all subjects:

- Overview of adverse events summarized by relationship and deaths (number and % of subjects who died, with any AE, any SAE, fatal SAEs, AEs leading to dose reduction/interruptions, AE leading to treatment discontinuation)
- AEs by SOC and PT, summarized by relationship (all AEs and AEs related to study treatment).
- SAEs summarized by relationship (all SAEs and SAEs related to study treatment) and severity.
- AEs leading to study treatment discontinuation (all AEs and AEs related to study treatment).
- AEs leading to study treatment dose reduction/interruption.

The following listings will be produced:

- All adverse events (safety set)
- All serious adverse events (safety set) (including those from the pre and post-treatment periods)
- Adverse events among subjects who were not treated (screening failure subjects)

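### As worded, the SAP's six combined ALT/AST–bilirubin rows omit any subject with exactly one transaminase above ULN at baseline; the second heading should say *or*

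*SAP*

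**What the plan says.** SAP 2.8.3 first lists single-parameter rows (ALT or AST above 3, 5, 8, 10 and 20 times ULN; total bilirubin above 2 and 3 times ULN). It then gives six combined rows in two blocks.

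- **Block 1** is for subjects with AST and ALT both at or below ULN at baseline. Its three rows require ALT or AST above 3x ULN with bilirubin above 2x ULN: overall, with ALP at least 2x ULN, and with ALP below 2x ULN.
- **Block 2** opens "For subjects with AST and ALT > ULN at baseline (Bsl". It has the same three rows, but the transaminase condition carries an asterisk and bilirubin must exceed both 2x baseline and 2x ULN.

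The asterisked note begins "Elevated AST or ALT defined as" and has two branches: above 3x ULN where baseline was at or below ULN, and above 3x baseline or 8x ULN where baseline was above ULN. It is attached only to Block 2.

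The protocol groups the elevated-baseline subjects with *or*. Section 6.5.2.1 has "For subjects with elevated AST or ALT or TBIL value at baseline". Table 6-3, under combined elevations, has "For participants with elevated baseline AST or ALT or total bilirubin value". Inclusion criterion 8 sets separate limits for AST and ALT, each below 3x ULN (below 5x ULN with liver metastasis).

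**The concern.** The two headings look complementary but are not. The complement of both enzymes being normal is at least one being raised, whereas Block 2 asks for both to be raised. A subject who enters with, say, ALT above ULN and AST normal is left out of both blocks. If that subject later has a joint transaminase and bilirubin rise, no combined row counts it.

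These rows are the SAP's only purely laboratory-based count of the joint event. Hepatotoxicity and hepatitis are adverse events of special interest (Protocol 10.2.1), and enrollment was halted for lack of tolerability of the combination. The joint liver count is therefore one that readers of the study report will look at.

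**Working it through.** The plan states no figure to reproduce here; the check is one of logic.

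**1. Coverage of baseline patterns.** Each enzyme is either at or below ULN, or above it, which gives 2 x 2 = 4 patterns.

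| AST | ALT | Block 1 | Block 2 as worded | Block 2 with *or* |
|---|---|---|---|---|
| ≤ ULN | ≤ ULN | yes | no | no |
| ≤ ULN | > ULN | no | no | yes |
| > ULN | ≤ ULN | no | no | yes |
| > ULN | > ULN | no | yes | yes |

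As worded, 2 of 4 patterns are placed. With *or* in Block 2 only, 4 of 4 are placed, each exactly once. Reading *and* loosely as *either* in both headings does not help, because the two mixed patterns would then fall in both blocks.

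**2. The footnote.** Under the literal Block 2 heading both enzymes are above ULN, so the branch for an enzyme at or below ULN at baseline can never apply. With *or*, it applies to the normal enzyme in each mixed pattern.

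**3. Two constructed cases** (multiples of ULN). Both have baseline ALT 1.5, AST 0.8 and bilirubin 0.8, with later bilirubin 2.5 and ALP 1.2. The bilirubin condition holds in both: 2.5 > 2 x 0.8 = 1.6 and 2.5 > 2.

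- *Case A:* ALT rises to 4.8 and AST is 0.9. The ALT trigger is the lower of 3 x 1.5 = 4.5 and 8; 4.8 > 4.5. Rows entered: 0 of 6 as worded, 2 of 6 with *or* (the overall row and the row with ALP below 2x ULN).
- *Case B:* ALT 2.0, AST 3.5. ALT does not reach 4.5. AST was normal at baseline, so its trigger is 3; 3.5 > 3. Rows entered: 0 of 6 as worded, 2 of 6 with *or*, through the otherwise unreachable branch.

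**4. Denominators.** SAP 2.1 says "Percentages will be calculated using the number of patients in the relevant population or subgroup as the denominator". Take the 31 treated subjects (Protocol 4.1), assume baseline AST and ALT are available for all, and let m be the number with a mixed baseline. If the baseline group is the denominator, the two denominators sum to 31 − m as worded and to 31 with *or*. The documents do not give m; for assumed m = 0, 1, 3, 6 the literal sum is 31, 30, 28, 25. If the whole Safety Set is the denominator, it is 31 for every row and nothing changes.

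**The case against.** **The intended reading is plain from the same section.** The footnote shows that *or* was meant, and derived variables are specified in a separate programming document that is not public. The tables may well be programmed correctly. That stands as to the output: nothing here shows that any table will be wrong. It does not remove the need to correct the text. SAP section 1 routes changes to the planned analysis through an amendment or addendum and exempts only minor formatting or spelling slips in the output shells.

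**The joint event has another planned route.** A reader might infer that such liver cases would disappear from the report. The documents do not support that.
- Protocol 6.5.2.1 requires cases that meet its laboratory criteria, are confirmed on repeat testing and have no alternative cause to be reported as an SAE under a named term for potential drug-induced liver injury. SAP 2.8.1 tabulates SAEs. Both constructed cases meet those criteria: A, 4.8 > 2 x 1.5 and > 3; B, 3.5 > 2 x 0.8 and > 3; bilirubin as above.
- Protocol 8.4.5 sends to the AE page "abnormal laboratory parameters which are clinically relevant and require an action to be taken with study treatment", and SAP 2.8.1 summarises "AEs leading to study treatment discontinuation (all AEs and AEs related to study treatment".
- Single values stay in the single-parameter rows and the shift tables. Protocol 12.5.2.2 also plans a "Listing of all laboratory data with values flagged to show the corresponding CTCAE v5.0 grades if applicable". SAP 2.8.3 itself names only a grade 3 or 4 listing, but SAP section 4 declares no change to the protocol's analyses.

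What remains is narrower: the SAE route depends on confirmation and causality, so it is not the same as a laboratory count.

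**The denominators need not be affected.** A reader might conclude that the percentages are necessarily based on too few subjects. SAP 2.1 allows either the population or the subgroup, and SAP 2.8 bases safety summaries on the Safety Set. The 31 − m sums are one reading only.

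**The protocol is an imperfect model.** Section 6.5.2.1 uses 2x baseline where the SAP footnote uses 3x, and both protocol rules also count raised baseline bilirubin as an elevated baseline. The SAP does not copy 6.5.2.1, so the footnote is the main evidence of intent and the protocol wording is supporting evidence. Table 6-3 is closer, with the same 3x baseline and 8x ULN multiples as the footnote.

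**Conclusion.** The concern holds as a wording error in SAP 2.8.3. Followed literally, the rule omits subjects with exactly one raised transaminase at baseline from all six combined rows and makes one footnote branch unusable. The footnote, supported by Protocol 6.5.2.1 and Table 6-3, shows that *or* was intended.

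Severity is minor. The effect is confined to descriptive safety rows in a single arm of 31; ORR, DCR and PFS are untouched. A count changes only if a mixed-baseline subject also has a joint elevation. The documents give no frequency for either, and the number of mixed-baseline subjects may be zero. The point concerns the SAP text, since the programming specifications and output shells are not available.

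**What to change.** In the second baseline heading of SAP 2.8.3, replace *and* with *or* between AST and ALT. State that the footnote applies to each enzyme according to its own baseline. Leave *and* in the first heading, where it is correct. Check that the programming specifications and output shells agree, and state whether the percentages use the baseline group or the Safety Set.

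This makes the two blocks exhaustive and mutually exclusive for AST and ALT. It does not align the SAP with the protocol on raised baseline bilirubin or on the 2x baseline multiple in Protocol 6.5.2.1; those are separate choices that this change does not require. The cost is one word and a clarifying sentence or two in the SAP. All the data are already collected.

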**Table 6-4 Clinical and diagnostic assessments for LFT abnormalities**

Disease	Assessment
Hepatitis A, B, C, E	IgM anti-HAV; HBsAg, IgM & IgG anti-HBc, HBV DNA; anti-HCV, HCV RNA, IgM & IgG anti-HEV, HEV RNA
CMV, HSV, EBV infection	IgM & IgG anti-CMV, IgM & IgG anti-HSV; IgM & IgG anti-EBV
Autoimmune hepatitis	ANA & ASMA titers, total IgM, IgG, IgE, IgA
Alcoholic hepatitis	Ethanol history, GGT, MCV, CD-transferrin
Nonalcoholic steatohepatitis	Ultrasound or MRI
Hypoxic/ischemic hepatopathy	Medical history: acute or chronic CHF, hypotension, hypoxia, hepatic venous occlusion. Ultrasound or MRI.
Biliary tract disease	Ultrasound or MRI, ERCP as appropriate.
Wilson disease (if <40 yrs old)	Ceruloplasmin
Hemochromatosis	Ferritin, transferrin
Alpha-1-antitrypsin deficiency	Alpha-1-antitrypsin

Other causes should also be considered based upon subjects' medical history (hyperthyroidism/ thyrotoxic hepatitis – T3, T4, TSH; CVD / ischemic hepatitis – ECG, prior hypotensive episodes; T1D / glycogenic hepatitis).

Obtain PK sample to determine exposure to study treatment.

Following appropriate causality assessments, as outlined above, the causality of the treatment is estimated as "probable" i.e. >50% likely, if it appears greater than all other possible causes of liver injury combined. The term "treatment-induced" indicates *probably caused* by the treatment, not by something else, and only such a case can be considered a DILI case and should be reported as an SAE.

All cases confirmed on repeat testing meeting the laboratory criteria defined above, with no other alternative cause for LFT abnormalities identified, should be considered as "medically significant," and thus, meet the definition of a serious adverse event (SAE) and should be reported as SAE using the term "potential drug-induced liver injury." All events should be followed up with the outcome clearly documented.

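### The SAP's combined liver rows follow only one of two protocol thresholds for raised baseline transaminases, so some subjects meeting the protocol's potential-DILI laboratory criteria are not identified as joint elevations

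*SAP*

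**What the plan says.** **Protocol 6.5.2.1** sets laboratory criteria for potential DILI. Its raised-baseline part opens "For subjects with elevated AST or ALT or TBIL value at baseline" and asks for "AST or ALT > 2 x baseline AND > 3.0 x ULN] OR [AST or ALT > 8.0 x ULN". Bilirubin must at the same time exceed both twice its baseline and twice the ULN. Under the text following Table 6-4, cases confirmed on repeat testing with no other cause "should be reported as SAE using the term" for potential drug-induced liver injury.

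**Protocol Table 6-3**, in its block on combined AST/ALT and bilirubin elevation, has a second limb that begins "For participants with elevated baseline AST or ALT or total bilirubin value". It uses AST or ALT above 3x baseline or above 8x ULN, whichever is lower. The bilirubin condition is the same as in 6.5.2.1, with a further proviso that there is no sign of cholestasis or hemolysis.

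**SAP 2.8.3, Liver function parameters**, has combined rows in two baseline groups. The second is headed "For subjects with AST and ALT > ULN at baseline (Bsl"). Its footnote defines elevated AST or ALT for this group as above 3x "Bsl or 8x ULN) if > ULN at baseline". Bilirubin must exceed 2x baseline and 2x ULN. The same table has single-parameter rows for ALT or AST above 3x, 5x, 8x, 10x and 20x ULN and for bilirubin above 2x and 3x ULN.

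**The concern.** Combined rows exist to show that a transaminase rise and a bilirubin rise occurred in the same person. For raised baselines, the protocol's own definition of potential DILI is wider than the rule the SAP tabulates, and the SAP does not say why it uses the narrower one. Some subjects whom the protocol sends for DILI work-up would therefore not be counted as joint elevations in the liver table.

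This matters because hepatotoxicity (capmatinib) and hepatitis (spartalizumab) are adverse events of special interest in Protocol 10.2.1, and because enrollment was halted for lack of tolerability of the combination. With a treated population this small, safety is a main remaining output and a single joint case is worth seeing.

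**Working it through.** No planned figure has to be reproduced; the check compares three rules.

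**Notation.** For one enzyme, let b be the baseline and v the on-treatment peak, both in multiples of ULN, with b > 1. The SAP's 8x ULN is read as above 8x ULN. The bilirubin condition is the same in all three places, so only the transaminase part differs.

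- Protocol 6.5.2.1: (v > 2b and v > 3) or v > 8, so the trigger is v > min(max(2b, 3), 8).
- SAP footnote: v > 3b or v > 8, so the trigger is v > min(3b, 8).
- Table 6-3, raised-baseline limb: v > min(3b, 8), the same as the SAP.

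**Nesting.** If b > 1 and v > 3b, then v > 3 and v > 2b. Every value that meets the SAP rule therefore meets 6.5.2.1, but not the reverse. A grid with b from 1.01 to 4.99 and v from 0.01 to 25.00, in steps of 0.01, agrees: no point met the SAP rule alone, many met 6.5.2.1 alone, and the SAP and Table 6-3 thresholds agreed everywhere.

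**Size of the band.** The SAP rule misses max(2b, 3) < v ≤ min(3b, 8).

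| Baseline (x ULN) | 6.5.2.1 trigger | SAP trigger | Gap (x ULN) |
|---|---|---|---|
| 1.2 | >3.0 | >3.6 | 0.6 |
| 1.5 | >3.0 | >4.5 | 1.5 |
| 2.0 | >4.0 | >6.0 | 2.0 |
| 2.5 | >5.0 | >7.5 | 2.5 |
| 3.0 | >6.0 | >8.0 | 2.0 |
| 3.5 | >7.0 | >8.0 | 1.0 |
| 4.0 or more | >8.0 | >8.0 | 0 |

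The gap is widest where 3b = 8, at b = 2.67: 8 − 5.33 = 2.67x ULN. It closes where 2b = 8, at b = 4. Inclusion criterion 8 admits AST and ALT below 3x ULN, or below 5x ULN with liver metastasis, so baselines in this range can enter.

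**Example.** Both enzymes are above ULN at baseline, with ALT at 2x ULN and bilirubin normal. On treatment ALT reaches 5x ULN, AST stays at or below its own SAP threshold, and bilirubin reaches 2.5x ULN.

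- 6.5.2.1: 5 > 2 × 2 = 4 and 5 > 3, so the ALT part is met. Bilirubin at 2.5x ULN exceeds 2x ULN and, with a baseline of at most 1x ULN, 2x baseline. The laboratory criteria are met.
- SAP combined rows: 5 is not above 3 × 2 = 6 and not above 8. The subject is not counted.
- Other SAP laboratory outputs: the subject counts under ALT or AST >3x ULN and under bilirubin >2x ULN, and enters the shift tables, each test separately. Under SAP Table 5-3 both values are grade 2 (ALT >3 to 5x ULN, bilirubin >1.5 to 3x ULN), so the only laboratory listing in SAP 2.8.3, limited to grade 3 or 4, need not show the subject.

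**Denominator.** The safety set equals the full analysis set: anyone who received at least one dose of either drug. Protocol 4.1 gives 31 treated, made up of the 28 on the combination and the 3 who started on capmatinib alone. One case is 1/31 = 3.2%.

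**The case against.** The strongest reply is that the SAP has not departed from the protocol. Its raised-baseline thresholds are those of Table 6-3, the section neither cites 6.5.2.1 nor claims to count potential DILI, and the inconsistency lies between two protocol sections. That stands, and it is why reconciliation has to start in the protocol.

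A reader might infer that these subjects vanish from the safety outputs. They do not. The single-parameter rows and shift tables keep them, and a case confirmed without another cause is also reported as an SAE. Only the joint identification is lost.

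A reader might also expect the liver table and the SAE listing to agree once the thresholds match. They need not. The SAE requires repeat confirmation and exclusion of other causes, and its collection can run to 150 days after spartalizumab. The laboratory rows use values alone, up to 30 days after the last study treatment.

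Finally, a reader might call the two protocol thresholds a plain mistake. The documents do not settle this. For raised baselines, an earlier trigger for work-up and a later one for discontinuation could be intended. One could argue that the order reverses for normal baselines, because the grade-based limb of Table 6-3 starts at grade 2 bilirubin (>1.5x ULN) against >2x ULN in 6.5.2.1. But that assumes the grade-based limb is confined to normal baselines. The table joins its limbs with OR and does not say so.

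**Conclusion.** The point holds in a limited form and is a cheap improvement. For raised baselines, the SAP rule is strictly narrower than the 6.5.2.1 laboratory criteria. The combined rows miss joint elevations with a transaminase baseline between 1x and 4x ULN and a peak in the band shown, never above 8x ULN.

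The number of subjects affected cannot be computed, because the documents give no baseline liver-test distribution. It may be zero. Nothing in the documents says that the halt was for hepatic reasons or that a liver signal has been understated, and no efficacy result is touched.

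The example assumes both enzymes are raised at baseline, which isolates the multiplier. A subject with only one raised falls in neither SAP baseline group as worded; that is a separate gap and is not counted here.

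**What to change.** In SAP 2.8.3, keep the existing 3x-baseline rows. Beside them, add clearly labelled combined rows that count subjects meeting the Protocol 6.5.2.1 laboratory criteria, using that section's own baseline grouping. State in the footnote which protocol section each set of rows follows.

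Separately, the sponsor should reconcile Protocol 6.5.2.1, Protocol Table 6-3 and SAP 2.8.3, or state that the thresholds differ by intent. No clinical threshold is proposed here. Keeping both sets of rows means the table does not anticipate how that is settled.

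The cost is one more derived flag from laboratory data already collected, a few table lines, and a reported count that may be higher.
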